### 1.2.1.5 Secondary Outcomes

#### 1.2.1.5.1 Acute Effectiveness

AF termination or CL prolongation:

1. Termination of spontaneous or induced AF by ablation of the source of arrhythmia

	FIRMAP AF Statistical Analysis Plan		Rev: 01	Effective: 05JAN2016
---	-------------------------------------	--	---------	----------------------

2. Reduction of the mean AF rate (total time measured across 10 consecutive cycles in the coronary sinus divided by 10) by least 10% by ablation of the source of arrhythmia

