### 3 BACKGROUND AND RATIONALE

Atrial fibrillation (AF) is the most common sustained arrhythmia in man, and has an increasing population prevalence over time. Treatment is aimed at stroke prevention on the one hand, and amelioration of symptoms (palpitations, lightheadedness, dyspnea, fatigue) due to the arrhythmia. Medical therapy often fails to render a satisfactory response for the latter, prompting the search for alternative therapies. Surgical and, in the last 15 years, catheter ablation techniques have been devised to try to prevent episodes from starting. Groundbreaking work by Haïssaguerre showed that premature discharges or rapid repeated firing from the pulmonary veins (PVs) could trigger AF episodes and that electrical isolation of the PVs could potentially cure the patient of AF. PV isolation currently is a painstaking process consisting of delivering radiofrequency energy or cryoablation in the left atrium to isolate these veins. Such procedures take 2-5 hr. to be completed depending on the complexity of the individual case, and a majority of patients require a 2nd or even 3rd procedure to achieve acceptable antiarrhythmic results. Despite considerable investigative effort, the exact pathophysiology of how PV triggers initiate and or maintain episodes of AF has been elusive.

Recently, a novel mapping technology (RhythmView, Abbott, Menlo Park, CA) based upon the work by Narayan et al has been developed for analyzing atrial recordings during human AF, finding that >95% of cases demonstrate either a rapidly spinning rotor (small circuit) or very rapid focal impulse formation. Furthermore, they have shown that catheter ablation at these relatively circumscribed areas can significantly affect AF, either by substantial slowing of the rate or termination (to an atrial tachycardia or sinus rhythm). In the CONFIRM (CONventional vs Focal Impulse and Rotor Modulation) trial, patients were treated with either conventional mapping and ablation (largely PV isolation or PVI) vs ablation of rotors or sites of focal impulse formation as designated by the mapping algorithm, followed by conventional ablation (PVI). The authors found much higher acute and long-term efficacy when focal impulse and rotor modulation (FIRM procedure) was used (82.4 vs 44% freedom from AF at 24 months post procedure). Although CONFIRM was a controlled study, a randomized evaluation would be warranted.

---

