#### E. Additional Secondary Investigations

Secondary Endpoints (unpowered) include:

1. AF termination or CL prolongation, as identified by:
  - a. Termination of spontaneous or induced AF by ablation of the source of arrhythmia.
  - b. Reduction of the mean AF rate by at least 10% by ablation of the source of arrhythmia.
2. Single-procedure freedom from AF/AT recurrence from 3-12 months post index ablation procedure (with 90-day blanking period) (Long-Term Effectiveness).
3. Freedom from symptomatic AF/AT recurrence from 3-12 months post index ablation procedure (with 90-day blanking period).
4. Freedom from AF recurrence from 0 – 12 months post index ablation procedure (without 90-day blanking period) (Long-Term Effectiveness).
5. Freedom from AF recurrence at 12 months post index ablation procedure (can include repeat procedures) (Long-Term Effectiveness).

Additional Investigations (unpowered) include:

1. Total RF ablation time.
2. Total Radiation Exposure.
3. Repeat ablation procedure and associated hospitalizations.
4. Quality of Life, as measured by the EQ-5D and AFEQT.
5. Cost-effectiveness analysis.

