#### 2.3 Additional Secondary Investigations

Secondary Endpoints (unpowered) include:

1. AF termination or CL prolongation, as identified by:

- a. Termination of spontaneous or induced AF by ablation of the source of arrhythmia.
- b. Reduction of the mean AF rate by at least 10% by ablation of the source of arrhythmia.
- 2. Single-procedure freedom from AF recurrence from 3-12 months post index ablation procedure (with 90-day blanking period) (Long-Term Effectiveness).
- 3. Freedom from symptomatic AF/AT recurrence from 3-12 months post index ablation procedure (with 90-day blanking period).
- 4. Freedom from AF recurrence from 0 – 12 months post index ablation procedure (without 90-day blanking period) (Long-Term Effectiveness).
- 5. Freedom from AF recurrence at 12 months post index ablation procedure (can include repeat procedures) (Long-Term Effectiveness).

Additional Investigations (unpowered) include:

- 1. Total RF ablation time.
- 2. Total Radiation Exposure.
- 3. Repeat ablation procedure and associated hospitalizations.
- 4. Quality of Life, as measured by the EQ-5D and AFEQT.
- 5. Cost-effectiveness analysis.

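### SAP 1.2.1.5.1 gives the formula for mean cycle length under the name of mean AF rate, so its 10% reduction rule, if applied literally, credits faster AF and fails slower AF

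*SAP*

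**What the plan says.** SAP section 1.2.1.5.1 places this secondary outcome under the label "AF termination or CL prolongation". Item 1 is AF termination. Item 2 requires a fall of at least 10% in mean AF rate and explains that quantity in parentheses: "Reduction of the mean AF rate (total time measured across 10 consecutive cycles in the coronary sinus divided by 10) by least 10" percent.

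The endpoint appears three more times without a formula: in Protocol Table 2, in SAP section 2.3 and in Protocol section 15.2 E. The last of these reads "Reduction of the mean AF rate by at least 10% by ablation of the source of arrhythmia". The parenthesis in SAP 1.2.1.5.1 is therefore the only operational formula in either document.

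Two other places show the intended direction. The protocol's abbreviation list defines CL as cycle length. Protocol section 3 describes the favourable effect of ablating the sources as acting on AF "either by substantial slowing of the rate or termination".

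On status, SAP section 2.3 lists the endpoint under "Secondary Endpoints (unpowered) include".

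**The concern.** Dividing elapsed time by a count of cycles gives time per cycle. A rate is cycles per unit time. The parenthesis therefore describes the reciprocal of the quantity it is attached to, and a fall in one is a rise in the other. The label asks for a longer cycle, while the formula combined with the word reduction asks for a shorter one. Both cannot hold.

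An analyst who derives the variable from the formula as written would reverse this component. An analyst who notices the conflict would have to choose a correction that the SAP does not document, possibly after seeing data. The component measures slowing of AF, half of the acute effect that the protocol's background puts forward for FIRM-guided ablation, so its direction should be beyond doubt.

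**Working it through.** The plan derives no figure from this rule, so there is nothing to reproduce. The check is one of units and direction.

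**Inputs**
- T = total time in ms of 10 consecutive coronary sinus cycles (SAP 1.2.1.5.1 item 2).
- Threshold: a reduction of at least 10% (same item).
- Baseline cycle length: not given in the documents. 200 ms is assumed for illustration, with 150, 180 and 220 ms as a range. The percentages do not depend on it.

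**Formulas** (0 = before ablation, 1 = after)
- The SAP quantity is M = T / 10, in ms per cycle, which is mean cycle length.
- Rate is R = 60,000 / M, in cycles per minute.
- Literal rule: M1 ≤ 0.90 × M0. Then R1 ≥ R0 / 0.90 = 1.111 × R0, so AF must be at least 11.1% faster.
- Rate rule, as the words state it: R1 ≤ 0.90 × R0. Then M1 ≥ M0 / 0.90 = 1.111 × M0, so cycle length must be at least 11.1% longer.

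No patient can meet both rules. Every patient who meets the rate rule fails the literal one, and the reverse.

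**Results from 200 ms (60,000 / 200 = 300/min)**

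| Cycle length after ablation | Rate | Change in rate | Change in SAP quantity | Literal rule | Rate rule |
|---|---|---|---|---|---|
| 180 ms | 333.3/min | +11.1% | −10.0% | success | failure |
| 220 ms | 272.7/min | −9.1% | +10.0% | failure | failure |
| 222.2 ms | 270/min | −10.0% | +11.1% | failure | success |
| 240 ms | 250/min | −16.7% | +20.0% | failure | success |

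**Other baselines**

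| Baseline | Scored success by the literal rule (10% shorter) | Scored failure by the literal rule (rate 10% lower) |
|---|---|---|
| 150 ms | 135 ms | 166.7 ms |
| 180 ms | 162 ms | 200 ms |
| 220 ms | 198 ms | 244.4 ms |

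**Scale of the threshold.** A 10% lower rate is a cycle 1 / 0.9 − 1 = 11.1% longer. A 10% longer cycle is a rate only 1 − 1 / 1.1 = 9.1% lower. From 200 ms the two cut-offs are 222.2 and 220 ms, a gap of 2.2 ms.

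**The case against.** The strongest reply is that the parenthesis only describes the measurement (site and averaging window) and does not replace the words it qualifies. The operative words are a reduction in rate, the label says prolongation, and Protocol Table 2, Protocol 15.2 E and SAP 2.3 all give the right direction. A programmer coding an outcome labelled cycle length prolongation might well see the slip. This stands as far as it goes: the reversal is conditional on literal use of the formula. It does not remove the error, because the only formula in the documents still yields the wrong quantity for the name it carries.

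A reader might also infer stronger points, which the documents do not support:

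- *That the trial means to count acceleration as success.* The label, the repeated rate-reduction wording and the protocol's background all say otherwise.
- *That the 10% threshold is seriously ambiguous.* Every statement of the endpoint puts the 10% on rate, and none sets a 10% lengthening of the cycle. The gap between the two scales is small in any case.
- *That results in both arms would be reversed.* The criterion concerns ablation of the arrhythmia source, and Protocol Table 5 restricts source diagnosis to FIRMap patients. The documents do not say how the component applies to the PVI arm.
- *That the protocol needs amending.* Its wording carries no formula and points the right way.

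**Conclusion.** The definition is wrong as written. SAP 1.2.1.5.1 item 2 calls mean cycle length a rate. Applied literally, its rule passes AF that has become at least 11.1% faster and fails every degree of slowing. This follows from the units alone and holds at any baseline; only the example values in ms rest on the assumed 200 ms.

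The scope is narrow: one component of an unpowered secondary endpoint, for which neither document specifies a hypothesis or test. The AF-termination component, the formally tested acute endpoint (rotor elimination or vein isolation, SAP 2.2.2), the safety endpoints, the primary endpoint and the sample size do not depend on it. It is an inconsistency of definition and unit that should be corrected before the variable is programmed, and it does not threaten the trial's main conclusion.

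**What to change.** Replace the text of SAP 1.2.1.5.1 item 2 with wording such as:

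> Mean AF cycle length = total time of 10 consecutive coronary sinus cycles / 10. Mean AF rate = 60,000 / mean cycle length (ms). The criterion is met if mean AF rate falls by at least 10% from its pre-ablation value (equivalently, cycle length lengthens by at least 11.1%, that is, to at least the pre-ablation value divided by 0.9).

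This keeps the threshold on the rate scale that every statement of the endpoint uses. SAP 2.3, Protocol Table 2 and Protocol 15.2 E can stay as they are, so no protocol amendment, with the approvals described in Protocol 12.1, is needed.

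The cost is a few lines in the SAP. Separately, the sponsor should confirm that coronary sinus intervals before and after ablation are captured. Neither the ablation data row of Protocol Table 5 nor the intra-procedure measurements in Protocol 9.2 C lists AF cycle length or rate, so it should not be assumed that the data are already available.

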#### ***1.2.1.5.2 Long-Term Effectiveness***

1. Single-procedure freedom from AF/AT recurrence from 3-12 months post index ablation procedure (with 90-day blanking period).
2. Freedom from symptomatic AF/AT recurrence from 3-12 months post index ablation procedure (with 90-day blanking period).
3. Freedom from AF recurrence from 0-12 months post index ablation procedure (without 90-day blanking period).
4. Freedom from AF recurrence at 12 months post index ablation procedure (can include repeat procedures).

#### ***1.2.1.5.3 Quality of Life***

Impact on quality of life, using patient-reported outcome instruments (EQ-5D and AFEQT), within treatment groups (change from pre-procedure to post-procedure follow-up timepoints) and between treatment groups. Analysis will be performed if primary endpoints are met.

#### ***1.2.1.6 Additional Evaluations***

##### ***1.2.1.6.1 Total RF Ablation Time***

Total RF ablation time as measured by total time of ablation lesion applications, from first ablation lesion to end of last lesion, will be documented. These values will be compared between the FIRM-guided and conventional ablation groups.

If ablation for AT/atrial flutter is pursued, this ablation time will be documented separately

##### ***1.2.1.6.2 Total Radiation Exposure***

As above, these values will be compared between the FIRM-guided and PVI groups.

##### ***1.2.1.6.3 Repeat procedure and hospitalization***

Any information regarding repeat procedures and re-hospitalizations will be collected and compared between groups

##### ***1.2.1.6.4 Economic Analysis***

Cost-effectiveness analysis based on clinical and patient-reported outcomes and resource utilization. Analysis will be performed if primary endpoints are met.

	FIRMAP AF Statistical Analysis Plan		Rev: 01	Effective: 05JAN2016
---	-------------------------------------	--	---------	----------------------

## 2 Statistical Methods

### 2.1 General Analysis Principles

All primary endpoint analyses will be conducted under the principle of “Intention-To-Treat” (ITT), where each subject randomized to a treatment group who has had a mapping and/or ablation catheter inserted shall be considered part of the ITT group. As a secondary exploratory analysis, a “Per Protocol” (PP) analysis may be performed with a subgroup of the ITT group who have no major protocol deviations reported.

### 2.2 Study Endpoints

#### 2.2.1 Long-Term Effectiveness (Primary effectiveness endpoint)

The primary effectiveness endpoint is single-procedure freedom from AF/AT recurrence from 3-12 months after the index AF ablation procedure (with 90-day blanking period)..

The hypothesis to be tested is the recurrence rate for FIRM-guided AF ablation is not inferior to that experienced by the conventional AF ablation arm.

The statistical hypothesis for this endpoint is operationalized as follows:

$$H_0: \Delta > .15$$

$$H_A: \Delta < .15$$

$$\alpha = .05 \text{ (two-tailed)}$$

Where:

$$\Delta = p_C - p_F$$

$p_C$  = Proportion free from AF recurrence at twelve (12) months post index ablation procedure for the conventional AF ablation arm (.50)

$p_F$  = Proportion free from AF recurrence at twelve (12) months post index ablation procedure for the FIRM-guided AF ablation arm (.55)

The non-inferiority margin for this hypothesis is 15% (.15). If the lower limit of the two-sided 95% confidence interval calculated for the difference in proportions ( $\Delta$ ) is less than .15, the null hypothesis will be rejected and evidence in favor of the alternative (FIRM-guided ablation for atrial fibrillation is not inferior to conventional ablation for atrial fibrillation) affirmed.

This non-inferiority margin was chosen based on that used in the FreezeAF and VGLB trials.

 Luik, Armin MD, et. al. (2010). Rationale and design of the FreezeAF trial: A randomized controlled noninferiority trial comparing isolation of the pulmonary veins with the cryoballoon catheter versus open irrigated radiofrequency ablation in patients with paroxysmal atrial fibrillation. American Heart Journal. 159(4):555-560.

The proportion of successes in each treatment arm shall be estimated using Kaplan-Meier survival estimation.

### **2.2.2 Acute Effectiveness (Secondary effectiveness endpoint)**

The acute success of each arm shall be determined by:

1. A subject in the FIRM-guided ablation arm shall be classified as an acute success upon elimination of all identified atrial fibrillation rotors.
2. A subject in the conventional ablation arm shall be classified as an acute success upon isolation of all pulmonary veins.

The proportion of successes in each arm will be calculated as follows:

$$\frac{n}{N}$$

Where:

$n$  = the total count of “successful” subjects in the arm in question

$N$  = the total count of subjects for that arm in the ITT group

The statistical hypothesis for this endpoint is operationalized as follows:

$$H_0: p_F = p_C$$

$$H_A: p_F \neq p_C$$

$$\alpha = .05 \text{ (two-tailed)}$$

Where:

$p_F$  = the proportion of “successes” in the FIRM-guided ablation arm

$p_C$  = the proportion of “successes” in the conventional ablation control arm

The analysis to be performed for this endpoint will be a Chi-square test of Independence.

### **2.2.3 Acute Safety**

The acute safety success of either treatment arm is defined as freedom from serious adverse events related to the procedure within seven (7) days of the index procedure.

The proportion of successes in each arm will be calculated as follows:

$$\frac{n}{N}$$

Where:

---

 Dukkipati,, Srinivas R. MD, et. al. (2015). Pulmonary Vein Isolation Using the Visually Guided Laser Balloon. Journal of the American College of Cardiology. 66(12):1350-1360.

	FIRMAP AF Statistical Analysis Plan		Rev: 01	Effective: 05JAN2016
---	-------------------------------------	--	---------	----------------------

$n$  = the total count of subjects presenting freedom from serious adverse events related to the procedure within seven (7) days of the index procedure.

$N$  = the total count of subjects in that arm in the ITT group

The statistical hypothesis for this endpoint is operationalized as follows:

$H_0: p_F = p_C$

$H_A: p_F \neq p_C$

$\alpha = .05$  (two-tailed)

Where:

$P_F$  = the proportion of “successes” in the FIRM-guided ablation arm

$p_C$  = the proportion of “successes” in the conventional ablation control arm

The analysis to be performed for this endpoint will be a Chi-square test of Independence.

#### 2.2.4 Long-Term Safety

Long-term safety is defined as freedom from serious adverse events related to the procedure (including those related to repeat procedures) within one year of the index procedure.

The statistical hypothesis for this endpoint is operationalized as follows:

$H_0: p_F = p_C$

$H_A: p_F \neq p_C$

$\alpha = .05$  (two-tailed)

Where:

$P_F$  = the proportion of subjects free from serious adverse events related to the procedure (including those related to repeat procedures) within one year of the index procedure in the FIRM-guided ablation arm

$p_C$  = the proportion of subjects free from serious adverse events related to the procedure (including those related to repeat procedures) within one year of the index procedure in the conventional ablation control arm

The proportion of successes in each treatment arm shall be estimated using Kaplan-Meier survival estimation.

#### 2.3 Additional Secondary Investigations

Secondary Endpoints (unpowered) include:

1. AF termination or CL prolongation, as identified by:

- a. Termination of spontaneous or induced AF by ablation of the source of arrhythmia.
- b. Reduction of the mean AF rate by at least 10% by ablation of the source of arrhythmia.
- 2. Single-procedure freedom from AF recurrence from 3-12 months post index ablation procedure (with 90-day blanking period) (Long-Term Effectiveness).
- 3. Freedom from symptomatic AF/AT recurrence from 3-12 months post index ablation procedure (with 90-day blanking period).
- 4. Freedom from AF recurrence from 0 – 12 months post index ablation procedure (without 90-day blanking period) (Long-Term Effectiveness).
- 5. Freedom from AF recurrence at 12 months post index ablation procedure (can include repeat procedures) (Long-Term Effectiveness).

Additional Investigations (unpowered) include:

- 1. Total RF ablation time.
- 2. Total Radiation Exposure.
- 3. Repeat ablation procedure and associated hospitalizations.
- 4. Quality of Life, as measured by the EQ-5D and AFEQT.
- 5. Cost-effectiveness analysis.

## 2.4 Power and Sample Size Estimation

Since the primary objective of this study relates to the long-term effectiveness of FIRM-guided ablation versus conventional ablation for atrial fibrillation (AF), power and sample size estimates have been calculated relative to that endpoint only. We anticipate enrolling 77 subjects in each treatment arm, plus an additional 8 subjects per arm to account for possible drop-outs / lost to follow-ups, for a total of 170 subjects (in approximately 20 sites).

Description	Assumptions
FIRM Group Freedom from recurrence of AF at 3 months	.55
CONVENTIONAL Group Freedom from recurrence of AF at 3 months	.50
Probability of Type I error (¶) (two-sided test)	.05

Minimum Total Sample Size (includes 10% adjustment for drop-outs and losses to follow-up)	170 (85 per group)
--	--------------------

With 77 subjects in each group, the lower limit of the observed one-sided 95.0% confidence interval will be expected to exceed -0.150 with 80% power when the Standard proportion,  $p_C$ , is 0.500 and the Test expected proportion,  $p_F$ , is 0.550; results are based on 1000 simulations using the Newcombe-Wilson score method to construct the confidence interval. In order to account for potential drop-outs and losses to follow-up, an additional 10% (16) will be added to the total sample size, for a final sample size of 170 (85 per group).

This power and sample size calculation was performed using NQuery 7.0 on the Microsoft Windows 10 operating system.

## 2.5 Missing Data and Lost to Follow-Up (Censoring)

No imputations or last observation carried forward (LOCF) will be conducted in this study. For purposes of the long-term primary safety and effectiveness endpoints, subjects missing safety or effectiveness data or lost to follow-up will be censored at their latest visit prior to the missing safety or effectiveness data.

For all other analyses, (acute safety and effectiveness), two presentations will be completed, one where the subject missing acute safety or effectiveness data or lost to follow-up will be excluded from the analysis, and another where that individual will be counted as a “failure” for the purpose of endpoint analysis. Both results will be presented.

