**Table 1 – Primary Effectiveness Endpoint**

Endpoint	Definition
Long term success	
Single-procedure freedom from AF/AT recurrence from 3-12 months post index ablation procedure (with 90-day blanking period).
 
* Freedom from AF/AT recurrence is defined as no documented episodes of AF/AT > 30 seconds with conventional non-invasive monitoring. In the case of a cardiac implanted electronic device (CIED), freedom from AF recurrence is defined as no documented episodes of AF/AT > 30 seconds in a 72-hour window at the follow-up visits in addition to any symptomatic episodes with documented AF > 30 seconds. AT recurrence does not include episodes of CTI (cavotricuspid isthmus) dependent flutter.

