#### **7.6 CONTACT FOR FOLLOW-UP AND LOSS TO FOLLOW-UP**

Subjects who miss a study visit should be contacted immediately by the Investigational Site to determine the reason for the missed visit and to reschedule the visit as soon as possible to meet the study visit window. If the subject cannot be located after 3 attempts through a variety of communication modes (phone, email, letter), then the subject will be considered lost to follow-up. The investigational sites should collect contact information (home phone, cell phone, fax, email, home address, etc.) from the subject in order to minimize loss to follow-up. All attempts to contact the subjects will be documented and retained in the subject study record.

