### 9.3 FOLLOW-UP REQUIREMENTS

- ***Follow-Up Visit Schedule***

Each enrolled subject will return for visits with the electrophysiologist in accordance with Table 8 below. The day of the study procedure represents Day 0. Study visits that do not occur within the below time windows will be considered protocol deviations.

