**Table 7 Follow-up (FU) Visit Windows**

Visit	Allowed Visit Date Range
Day 7 to 10 days (Phone or visit)	N/A
3 months (90 days)	± 2 weeks
6 months (180 days)	± 2 weeks
12 months (360 days)	± 4 weeks

- ***Resolution Period***

Following ablation treatment, subjects will undergo a 90-day “resolution” period (aka “blanking period”) where medical therapy may be optimized and where any of the procedurally-derived arrhythmias that commonly follow ablation procedures may resolve. During this period, adverse events will be accumulated but primary efficacy measurements will not be performed. In case of repeat ablation is solely for treatment of common type (cavo-tricuspid isthmus dependent) flutter, the patient has not failed the primary long-term efficacy endpoint.

*Note: During the 90-day resolution period, medications may be adjusted as medically indicated, and as indicated in above section. Any clinically indicated changes must be documented along with the reason for change.*

- ***Anti-arrhythmic Medications***

Anti-arrhythmic medications can be discontinued anytime from Day 91 to Day 180 post-procedure. The date of discontinuation will be determined by each investigator on a patient-by-patient basis, but must occur sometime from Day 91 to Day 180 post-procedure.

- ***Recurrence of AF***

If re-ablation for AF (not including common type atrial flutter) is necessary after documentation of the recurrent arrhythmia has

occurred, the patient will be considered a primary efficacy study failure but still followed up for AF burden.

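### SAP 2.5, read literally, censors a subject at the visit before a missing recording even when a later documented recurrence makes that subject a primary failure under the protocol

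*SAP*

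**What the plan says.** SAP 2.5 rules out imputation. It then gives one rule for long-term safety and long-term effectiveness: "subjects missing safety or effectiveness data or lost to follow-up" "will be censored at their latest visit prior to the missing safety or effectiveness data". Missing data and loss to follow-up are named as two separate triggers. SAP 2.2.1 estimates success in each arm by Kaplan-Meier, the target being "Proportion free from AF recurrence at twelve (12) months post index ablation procedure".

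The protocol defines failure by what is documented. In Table 1, "Freedom from AF/AT recurrence is defined as no documented episodes of AF/AT" longer than 30 seconds, over months 3 to 12. Under section 9.3, if AF re-ablation is needed after a documented recurrence, "the patient will be considered a primary efficacy study failure but still followed up for AF burden".

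A missed visit is not the same as loss. Protocol 7.6 tells sites to contact the subject and "to reschedule the visit as soon as possible to meet the study visit window", and a subject is lost only after three failed contact attempts. A late visit is not missing data either: "Study visits that do not occur within the below time windows will be considered protocol deviations".

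**The concern.** Take a subject whose 6-month 72-hour recording is never obtained and who has AF on the 12-month recording. The protocol calls this subject a failure. The literal SAP rule censors the same subject, event-free, at the 3-month visit (if there was no unscheduled visit in between). A subject whose 3-month recording is never obtained would be censored at discharge or the Day 7-10 contact, before the 3-12 month window opens, and would contribute nothing to it.

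This is the only powered endpoint. The plan leaves it to whoever programs the analysis to decide which subjects count as failures. The same sentence governs long-term safety (SAP 2.2.4), so a procedure-related SAE reported after a gap could also be dropped.

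**Working it through.** **1. The texts side by side.** SAP 2.5 has no clause for data that resume and none giving a documented event precedence. SAP 1.2.1.4, 2.2.1 and 2.6 do not supply one. Two readings are therefore open:
- literal: everyone with a gap is censored before it;
- softer: only subjects with no documented event are censored there.

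**2. The plan's own figure.** With pC = .50, pF = .55, margin .15 and a one-sided 95% limit, the sample-size formula returns 77 per arm. Exact enumeration of the Newcombe-Wilson limit at 77 gives power .806, so the stated 80% is reproduced. With the two-sided 95% interval of SAP 2.2.1, power at 77 is .707.

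**3. Assumptions (none is in the documents).** The 6-month recording is never obtained in m = 5, 10 or 20%. Of failures, 35% are first found at 12 months, 32.5% at the 6-month visit, and 32.5% through symptoms spread evenly over Days 91-360. Of the symptomatic failures, (180 - 90)/(360 - 90) = 1/3 are documented before Day 180 and still count. The literal rule therefore discards g = 1 - .325/3 = .892 of failures in subjects with a gap.

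Let p be the true success rate, and m0 and m1 the gap rates in subjects without and with recurrence. If recurrences at a missed visit are documented later, then to a close approximation:
- literal: S = p(1 - m0) / [p(1 - m0) + (1 - p)(1 - g·m1)]
- softer: S = p(1 - m0) / [p(1 - m0) + (1 - p)]

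**4. Gaps unrelated to outcome.** Documented recurrences discarded by the literal rule, g·m: 4.5, 8.9 and 17.8%. At m = .10:
- control: .45/(.45 + .50 × .9108) = .497
- FIRM at the margin (.35): .315/(.315 + .65 × .9108) = .347
- difference: .150

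Simulation over 12-month shares of 20 to 50% gives .149-.151 throughout. The softer reading turns a true .50 into .475/.975 = .487, .45/.95 = .474 or .40/.90 = .444.

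**5. Power under the literal rule.** Simulated trials had 85 per arm, 8/85 = 9.4% lost in addition to the gaps, Greenwood standard errors, and non-inferiority declared when the upper limit for pC - pF is below .15.

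| Interval | No gaps | 5% | 10% | 20% | Events after gaps counted |
|---|---|---|---|---|---|
| two-sided 95% | .71 | .69 | .67 | .62 | about .71 |
| one-sided 95% | .81 | .79 | .77 | .73 | about .81 |

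Hand check (two-sided): n = 77(1 - m), SE = √[(.50 × .50 + .55 × .45)/n], power = Φ(.20/SE - 1.96). This gives .70 with no gaps, then .68, .66 and .60.

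**6. Gaps related to outcome, true deficit .15.** If subjects with recurrence miss twice as often in both arms (base rate 10%), control reads .45/(.45 + .50 × .8216) = .523 and FIRM .315/(.315 + .65 × .8216) = .371. The difference is .152, slightly away from non-inferiority.

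If the doubling occurs in the FIRM arm only, the result depends on how it is set up:
- The 5, 10 or 20% is a base rate, doubled in FIRM subjects with recurrence. At 10%: .497 - .371 = .126. Across the three rates the formula gives .139, .126, .092 and simulation .138, .126, .091.
- Each arm's overall rate is held at 5, 10 or 20%, so m0 = m/1.65 and m1 = 2m/1.65, because .35 + 2 × .65 = 1.65. At 10%: FIRM = .3288/(.3288 + .5797) = .362, difference .135. Across the three rates: .143, .135, .117.

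**7. If recurrences at the missed visit are never documented later.** Counting all documented events then overstates success by (1 - p) × m1 × .325. At a true .50 with random gaps this is .008, .016 or .033, and .006 to .04 as the 6-month share runs from 25 to 40%. The .15 deficit reads .15(1 - .325m) = .148, .145 or .140, while the literal rule stays at .149-.150. With FIRM-only doubling of a base rate, it reads .15 - .325(1.3m - .5m) = .137, .124 or .098, against .139, .126 or .092 under the literal rule. With overall rates held, it reads .145, .141 or .131 against .143, .135 or .117.

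**The case against.** Kaplan-Meier censoring ordinarily applies to subjects without an event. Protocol 9.3 calls re-ablated subjects failures and Protocol 12.5 has endpoint events adjudicated, so a subject with an adjudicated recurrence is not obviously missing effectiveness data. This makes the softer reading plausible. It does not put it in the SAP, and that reading has a fault of its own: it keeps failures after a gap and drops clean results after a gap.

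A reader might infer that the rule tilts the trial toward non-inferiority. The documents do not support that. With random gaps the literal rule leaves the difference unchanged, and with outcome-related gaps equal in both arms it moves slightly the other way. The tilt needs FIRM subjects with recurrence to miss recordings more often, and nothing in the documents suggests they would.

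A reader might also infer that any late visit triggers censoring. Sites must try to reschedule, and an out-of-window visit is a deviation. The rule bites only when a recording is never obtained.

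The power figures put the gaps on top of the full 9.4% loss. If gap subjects fall within the allowance of 8 per arm, the cost is smaller. This stands.

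The correction is not always nearer the truth. If recurrences at the missed visit are never documented later, the literal rule is closer under random gaps. It is also marginally closer with FIRM-only doubling at base rates of 5 and 10%. This stands as well.

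**Conclusion.** The point holds as a defect of wording with a limited numerical effect. Followed exactly, SAP 2.5 discards recurrences that the protocol counts as failures, and no other section overrides it. At an assumed 5 to 20% of never-obtained 6-month recordings, random with respect to outcome, the literal rule costs about 2 to 9 points of power and does not bias the comparison. The softer reading lowers a true .50 by about 1 to 6 points. The FIRM-only figures (.143 down to .117, or .138 down to .091, for a true .15) are conditional illustrations, not expectations. A missing 3-month recording has the same effect in kind and was not sized separately. All gap rates and detection patterns are assumptions. The change is worth making because the powered endpoint should follow the protocol's own definition of success, fixed before outcomes are seen.

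**What to change.** In SAP 2.5, state that:
- AF/AT documented after Day 90 and through the 12-month visit, or AF re-ablation after documented recurrence, counts as a failure regardless of any earlier missed visit or missing recording;
- a subject with no event and a later protocol 72-hour Holter or CIED interrogation stays at risk across the gap;
- censoring at the last such recording applies only when there is no event and no later recording;
- for long-term safety, a procedure-related SAE reported after a gap counts in the same way.

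Report by arm how many subjects lack a 3- or 6-month recording but have later ones, so that a reader can judge whether gaps differ between arms.

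The cost is a few SAP sentences and minor programming, with no new data or patients and no change to the planned sample size. The downside is that a missing recording followed by a clean one counts as event-free. If recurrences at missed visits are never documented later, arm-level success is overstated by about .01 to .04 (more if subjects with recurrence miss more often), and with random gaps a true .15 deficit reads about .14 to .148. That price comes with the Table 1 definition, which rests on documented episodes.
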